7.1. Data Handling and Storage

Documents will be retained at xxxx for 15 years, which is in compliance with the United States' Food and Drug Administration Code of Federal Regulations (21 CFR §312.62[c]).⁶³ Access to source documents may be permitted for trial-related monitoring and audits, when appropriate. Individual data for monitoring, carrying out quality control, and auditing biomedical research may be shared at the discretion of the study investigators. Data collection forms will be kept in a locked office (research coordinators) within a locked cabinet.

Data will be transcribed into Research Electronic Data Capture (REDCap), which is a secure, web-based application for data capture.⁶¹ REDCap can be installed in a variety of environments for compliance with such standards as HIPAA, 21 CFR Part 11, FISMA (low, moderate, high), and international standards. The REDCap Consortium is a collaborative, international network of more than 2,400 institutional partners in over 115 countries, with >590,000 total end-users conducting 450,000 ongoing research studies.

7.2. Quality Control and Assurance

A clinical research associate appointed by xxxx IRB may visit during the study to ensure proper conduct. Items for review may include:

- Informed consent forms and EFIC documentation
- Compliance with the study protocol and procedures
- Quality of data collected in the case report form
 - o Accuracy
 - Missing data
 - Consistency of the data with the source documents
- Management of the study drug
- Each visit will be recorded in a written monitoring report.

Quality control mechanisms within the REDCap data collection tool may be used to ensure the appropriateness of data.⁶¹ For example, a birthday resulting in an age of 185 years will be flagged.

8. Adverse Events

8.1. Definitions

Adverse Event (per FDA 21CFR312.32)

Adverse event means any untoward medical occurrence associated with the use of a drug in humans, whether or not considered drug related.

Serious Adverse Event (per FDA 21CFR312.32)

An adverse event is considered "serious" if, in the view of either the investigator or sponsor (when applicable), it results in any of the following outcomes:

- Death (*see below exception)
- Life-threatening adverse event
- Inpatient hospitalization (*see below exceptions) or prolongation of existing hospitalization
- Persistent or significant incapacity or substantial disruption of the ability to conduct normal life functions (disability)
- Congenital anomaly/birth defect

Important medical events that may not result in death, be life-threatening, or require hospitalization may be considered serious when, based upon appropriate medical judgment, they may jeopardize the patient or subject and may require medical or surgical intervention to prevent one of the outcomes listed in this definition (above).

*Exception to the above serious adverse event definitions:

 An adverse event that results in death is usually considered a serious adverse event. However, 40-50% of patients who survive to the hospital after OHCA will not survive their hospital stay as a result of their underlying clinical condition. Since death is a clinical outcome for this study, deaths will not be reported as serious adverse events unless the investigator deems them related to study drug or study procedures.

Unexpected Adverse Event (per FDA 21CFR312.32)

An adverse event is considered "unexpected" if it is not listed in the investigator brochure or is not listed at the specificity or severity that has been observed; or, if an investigator brochure is not required or available, is not consistent with the risk information described in the general investigational plan or elsewhere in the current application, as amended.

Ceftriaxone is an FDA approved medication and does not have an investigator brochure. Therefore, the risk information is being provided in the protocol and informed consent form.

In addition, the unexpected adverse event definition assumes a causal relationship to the study drug (ceftriaxone). If an adverse event is not considered of Reasonable or Definite Relatedness to the ceftriaxone, it would not be considered an unexpected adverse event.

Relatedness

Relatedness	Description			
Not	The temporal relationship between exposure and the adverse event is			
NOL	unreasonable or incompatible, and/or it is clearly due to extraneous causes			
	Must have both of the following 2 conditions, but may have reasonable or			
	temporal relationship to the intervention:			
Unlikely	1. Could readily have been produced by the subject's clinical state, or			
	environmental or other interventions			
	2. Does not follow known pattern of response to intervention			
	Two of the following are true:			
	1. Has a reasonable temporal relationship to intervention			
Reasonable	2. Could not possibly have been produced by the subject's clinical state			
	or have been due to environmental or other interventions			
	3. Follows a known pattern of response to intervention			
	All 3 of the following are true:			
	1. Has a reasonable temporal relationship to intervention			
Definitely	2. Could not possibly have been produced by the subject's clinical state			
	or have been due to environmental or other interventions			
	3. Follows a known pattern of response to intervention			

The relatedness of an adverse event to the study drug will be defined as follows:

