8.2. Reporting

Serious adverse events that meet the Xxxx IRB reporting requirements will be reported to the IRB and DSMB within five business days of principal investigator notification.

Serious adverse events resulting in death and that meet the Xxxx IRB reporting requirements will be reported to the IRB and DSMB within 48 hours of the principal investigator notification.

Unexpected adverse events deemed reasonably or definitely related to the study drug will be reported to the IRB and DSMB within five business days of the principal investigator notification.

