8.4. Study Specific Adverse Events

Adverse events are common in comatose OHCA patients occurring in >90%.⁶⁴ Adverse events may be the result of the clinical context or study drug. Adverse events that meet the "serious" definition in section 8.1 will be documented and assessed using the xxxx IRB reporting criteria.

Clinical events secondary to cardiac arrest will not be reported at any grade, since these are considered symptoms of the condition being studied. These may include:

- Septic shock
- Bleeding requiring transfusion
- Bradycardia requiring pacing
- Seizure confirmed on cEEG

Study specific adverse events that are expected secondary to ceftriaxone use will be reported as required per the definitions in section 8.1 and the table below. These include:

- Clostridium difficile-associated diarrhea
- Gallbladder toxicity

• Type one hypersensitivity reactions

Study Specific Serious Adverse Events	Definition
	Unexplained and new-onset ≥3 unformed stools
Clostridium difficile-associated diarrhea	in 24 hours with a positive Clostridioides difficile
	toxin gene polymerase chain reaction assay
	Diagnosed sonographically as an echo without
Gallbladder toxicity	acoustical shadowing suggesting sludge and the
	presence of ceftriaxone-calcium salt
	Acute symptom onset (minutes to hours)
	involving the skin, mucosal tissue, or both (e.g.,
	generalized hives, pruritus or flushing, swollen
Type and hypersensitivity reactions	lips-tongue-uvula) and at least one of the
Type one hypersensitivity reactions	following (a through c):
	a. Respiratory compromise
	b. Reduced blood pressure
	c. Signs of end-organ dysfunction

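### For a reaction with no known pattern, a related rating requires every other cause to be impossible, and one type of well-timed event fits no relatedness category, so most new reactions would miss the unexpected-event route

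*Combined protocol and SAP*

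**What the plan says.** The relatedness table in section 8.1 has four categories. Reasonable applies when "Two of the following are true" and Definitely when "All 3 of the following are true". Both rows list the same three criteria:

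- timing: "Has a reasonable temporal relationship to intervention";
- other causes excluded: a criterion that opens "Could not possibly have been produced by the subject" and goes on to name the clinical state, the environment and other interventions;
- the event follows a known pattern of response to the intervention.

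Unlikely needs both that another cause could *readily* have produced the event and that there is no known pattern. Not applies when the timing is unreasonable or incompatible, or the cause is clearly extraneous.

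The same section ties expectedness to this rating: "If an adverse event is not considered of Reasonable or Definite Relatedness to the ceftriaxone, it would not be considered an unexpected adverse event". Section 8.2 says that unexpected events rated reasonably or definitely "related to the study drug will be reported to the IRB and DSMB within five business days". A separate sentence in section 8.2 covers serious adverse events that meet the IRB's own requirements.

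**The concern.** The unexpected-event route should bring reactions that nobody anticipated to the IRB and DSMB quickly. A reaction of a kind never seen with ceftriaxone fails the known-pattern criterion by definition. It is then related only if the investigator can say that nothing else could possibly have caused it. These patients are comatose after cardiac arrest and, under sections 3.12.1 to 3.12.5, may receive cooling, sedatives, paralytics, antiepileptic and vasoactive drugs. That statement will seldom be possible.

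The Unlikely row uses a weaker standard than the Reasonable row, so the two do not meet and some events fall between them. Section 2.4 says this antibiotic has not been tested after out-of-hospital arrest, and section 3.6 allows enrolment without prior consent, so this part of the safety reporting should work as intended.

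**Working it through.** The plan gives no figure to reproduce. The check applies the section 8.1 rules to every combination of three inputs: timing (reasonable or not), other cause (impossible, possible but not ready, ready) and pattern (known or not). That gives 2 × 3 × 2 = 12 combinations. Not is taken here as triggered by timing. Its other limb, a clearly extraneous cause, does not reach a cause that is merely possible.

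With reasonable timing there are six combinations. The last column applies the change described under the fix.

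| Other cause | Known pattern | Current rating | After the change |
|---|---|---|---|
| Impossible | Yes | Definitely | Definitely |
| Possible, not ready | Yes | Reasonable | Reasonable |
| Ready | Yes | Reasonable | Reasonable |
| Impossible | No | Reasonable | Reasonable |
| Possible, not ready | No | None | Reasonable |
| Ready | No | Unlikely | Unlikely |

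1. With no known pattern, at most two criteria can hold. Definitely is out of reach, and Reasonable needs both timing and the exclusion of every other cause. One of the three no-pattern combinations is rated related.
2. The fifth row fails Reasonable (one criterion met), fails Unlikely (the other cause is not ready) and fails Not (timing is reasonable). It has no category.
3. With a known pattern, timing plus pattern already make two, so the rating is Reasonable or Definitely whatever the other cause.
4. Under the relatedness condition in section 8.1, the fifth and sixth rows cannot be unexpected events and so do not enter the five-business-day route in section 8.2.

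With unreasonable timing, all six combinations meet Not. Two also meet another category: impossible other cause with a known pattern also meets Reasonable, and a ready other cause with no known pattern also meets Unlikely. The categories therefore overlap as well as leaving a gap.

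After the change, two of the three no-pattern combinations with reasonable timing are rated related instead of one, and none is unclassified. These are counts of combinations, not of events.

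**The case against.** A reader might infer that new reactions are never reported as unexpected, or that the route is closed to exactly the events it exists for. The documents support neither.

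- A well-timed new reaction with no possible other cause is Reasonable and reportable.
- Having no known pattern is not the same as being unexpected. Section 8.1 judges expectedness by whether the event is listed, is listed at the observed specificity or severity, or is consistent with the risk information in the protocol and consent form. A recognised reaction that is unlisted, or listed at another severity or specificity, is unexpected yet qualifies through timing and pattern.
- The serious-event rule in section 8.2 does not require unexpectedness. It sets five business days, or 48 hours for death. The IRB requirements it relies on are not in the documents, so it can be neither assumed to cover the gap nor shown to miss it.
- The DSMB is unblinded (section 3.10). The interim harm comparison of serious events in section 8.3 has no stated relatedness filter.

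It is also tempting to cite section 8.4, "Adverse events are common in comatose OHCA patients occurring in >90"%, as proof that another cause is nearly always possible. That figure counts patients with any adverse event, and the section says such events may come from the clinical context or the study drug. It does not measure how often another cause can be ruled out for a given event.

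Nor do the documents establish that this scale decides which deaths are reported. Section 8.1 leaves that to whether the investigator deems a death related to study drug or procedures, and the table covers study drug only.

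These points limit the reach of the problem. They do not supply the missing category, and they leave non-serious reactions of a new kind with no other stated expedited route.

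**Conclusion.** The point holds in limited form. The missing category and the two-criterion requirement for no-pattern events follow directly from the wording of section 8.1 and need no assumption about rates. That most reactions of a new kind would miss the unexpected-event route is a judgement: it assumes that investigators apply *could not possibly* literally and that in this population some other cause can usually be imagined. No percentage can be attached from the documents.

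The exposure is mainly non-serious reactions new to the drug, plus any serious ones that the unseen IRB criteria do not capture. The primary efficacy analysis is not affected. The correction is worth making because the rule contradicts itself and costs little to repair.

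**What to change.** In section 8.1:

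1. In the Reasonable row only, change the second criterion from *could not possibly* to *could not readily*, matching the Unlikely row.
2. Leave *could not possibly* in the Definitely row. A reaction with no known pattern cannot reach that row, and section 8.2 treats both ratings alike. Loosening it would add no reports and would let Definitely stand beside a possible other cause.
3. Word the Reasonable row as at least two criteria, with Definitely taking precedence. After step 1, a well-timed, known-pattern event with a possible but not ready other cause meets all three Reasonable criteria without being Definitely, and should not fall into a new gap.
4. State that an unreasonable or incompatible temporal relationship is rated Not whatever the other criteria. This removes both overlaps, and it is needed because step 1 alone would widen the one between Not and Reasonable.

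The cost is a short protocol edit and a few more events reported to the IRB and DSMB. New events that are readily explained by the illness stay Unlikely, so the gain is confined to the unclassified group. Parts of the document are in the past tense. If enrolment has ended, recorded serious events that were rated Unlikely or left unrated can be re-rated under the amended table.

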8.2. Reporting

Serious adverse events that meet the Xxxx IRB reporting requirements will be reported to the IRB and DSMB within five business days of principal investigator notification.

Serious adverse events resulting in death and that meet the Xxxx IRB reporting requirements will be reported to the IRB and DSMB within 48 hours of the principal investigator notification.

Unexpected adverse events deemed reasonably or definitely related to the study drug will be reported to the IRB and DSMB within five business days of the principal investigator notification.

8.3. Study Drug Discontinuation

Study drug will be discontinued if:

- 1. Gallbladder toxicity occurs OR;
- 2. Withdrawal from the trial is in the patient's best interest OR;
- 3. Infection develops warranting a change in the antibiotic regimen OR;
- 4. Subject, POAHC, or LAR declines or revokes informed consent.

In the event of stopping the study drug, patients will continue to be followed for safety and efficacy outcomes, and will collect blood, sputum, and rectal samples for the inflammation and resistome assessments.

The independent DSMB will be empowered to stop the trial for under certain circumstances:

- 1. Efficacy
 - a. The trial will not be stopped for efficacy given the intermediate outcome of interest is pneumonia, rather than death or other concrete outcomes (e.g., stroke, myocardial infarction). Additionally, it will not allow for a complete assessment of the resistome or inflammation.
- 2. Harm
 - a. There is a statistically significant increased risk for serious adverse events, including *Clostridium difficile*-associated diarrhea, gallbladder toxicity, or type one hypersensitivity reactions, during the interim analysis of the first n=60 patients enrolled. The p-value threshold for harm will be set at 0.05.
- 3. Safety
 - a. Significant safety concerns emerge and the DSMB and IRB choose to pause or stop the trial.

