3.6. Informed Consent

Study investigators will approach the patient's Power of Attorney for Health Care (POAHC) or LAR to provide informed consent. Patients regaining consciousness will be asked for informed consent as soon as they are able to make a decision and have the capacity to do so. Consent may be obtained in person or via remote consent process.

In the event a patient's POAHC or LAR cannot be reached for informed consent within 30 minutes, the EFIC process will be initiated at XXXX only per the Food and Drug Administration's Guidance for Institutional Review Boards, Clinical Investigators, and Sponsors on Exception from Informed Consent Requirements for Emergency Research.³⁶ The requirements for a clinical trial to incorporate EFIC are as follows:

- The human subjects are in a life-threatening situation that necessitates urgent intervention;
- Available treatments are unproven or unsatisfactory;
- Collection of valid scientific evidence is necessary to determine the safety and effectiveness of the intervention;
- Obtaining informed consent is not feasible because the subjects are not able to give their informed consent as a result of their medical condition;
- The intervention must be administered before consent can be obtained from the subject's legally authorized representative;
- There is no reasonable way to identify prospectively individuals likely to become eligible for participation;
- Participation in the research holds out the prospect of direct benefit to the subjects; and
- The clinical investigation could not practicably be carried out without the waiver.

After a thorough community consultation and public disclosure, the IRB at XXXX deemed it was appropriate to conduct the trial. The EFIC process will be initiated after 30 minutes of trying to contact the POAHC or LAR

Subsequent to an EFIC enrollment, efforts to contact an LAR will continue. The research team will inform LAR at earliest opportunity of the subject's inclusion in the trial, the details of the investigation, other information in the informed consent document and consent to continue in the study will be sought. The LAR will be also be notified that they may discontinue the patient's participation without penalty or loss of benefits to which the subject is otherwise entitled. Patients enrolled in the study through the EFIC

process or LAR consent will be asked for informed consent as soon as they have the capacity to do so, preferably prior to hospital discharge.

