4.1. Specimen Handling and Transportation

Sputum sample and rectal swab will be collected prior to study drug initiation and 72-96 hours after administration of first dose of study drug (after study drug has been completed). A third rectal swab will be collected 144-168 hours after administering first dose of study drug or earlier in the case of death, comfort measures only or hospital discharge, after which no study procedures will be conducted. Missing time points do not disqualify patient for study participation and is not a protocol deviation. Total nucleic acids will be extracted and resistomes determined by shotgun metagenomic sequencing using super high-throughput methods. COVID-19 considerations are outlined in Appendix 16.7. Samples from non-XXXX hospitals may be stored and transported under various conditions not listed above but that are acceptable.

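### Section 8.3 continues follow-up and research sampling after consent is declined or revoked, or after withdrawal from the trial, which conflicts with section 3.6 and with its own reason 2

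*Combined protocol and SAP*

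**What the plan says.** Section 8.3 lists four alternative reasons for stopping study drug: gallbladder toxicity; withdrawal from the trial being best for the patient; an infection that calls for different antibiotics; and, as reason 4, "Subject, POAHC, or LAR declines or revokes informed consent". One sentence then covers what happens next, whichever reason applied: "In the event of stopping the study drug, patients will continue to be followed for safety and efficacy outcomes", and the trial "will collect blood, sputum, and rectal samples for the inflammation and resistome assessments".

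Section 3.6 treats consent as governing the whole of participation. After an EFIC enrolment the representative is told about the trial and "consent to continue in the study will be sought". The representative is also told that "they may discontinue the patient's participation without penalty or loss of benefits to which the subject is otherwise entitled". The patient is approached later: "Patients regaining consciousness will be asked for informed consent as soon as they are able to make a decision".

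Section 4.1 names the events that bring the last rectal swab forward and close study procedures: "or earlier in the case of death, comfort measures only or hospital discharge, after which no study procedures will be conducted". Revoked consent is not among them.

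**The concern.** Section 8.3 makes refusal or revocation of consent a trigger for a rule whose content is continued follow-up and continued invasive research sampling. Section 3.6 gives the representative the right to end participation, which is wider than ending study drug. A coordinator told by a family that consent is revoked cannot comply with both sections.

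This branch is foreseeable. Under EFIC, the representative and later the patient are asked after enrolment whether participation should continue, and some may say no. What is at stake is research blood, airway and rectal sampling without permission, prescribed by the protocol's own text, and the lack of any rule on what outcome follow-up may continue.

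Reason 2 has the same fault. A patient for whom leaving the trial is judged best is placed under a rule that keeps that patient in it.

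**Working it through.** **Step 1: the text.** No arithmetic decides the point, so the provisions are set side by side.

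| Provision | What it requires | Does it resolve reasons 2 and 4? |
|---|---|---|
| 8.3, list | Drug stops if any of four reasons applies | Puts drug-only stops and withdrawal in one list |
| 8.3, next sentence | Follow-up and all three sample types continue | No exception by reason |
| 3.6 | Representative may end participation; agreement to continue is sought after EFIC | Conflicts with 8.3 for reason 4 |
| 3.2 | Refused consent is an exclusion | No: it covers refusal before enrolment only |
| 4.1 | Procedures end at death, comfort care or discharge | No: revocation is not named |
| 4.1, 5.1, section 13 footnote | A missed time point is not a deviation | No: this excuses an omitted sample but does not prohibit taking it, and does not cover outcome follow-up |
| 6 and 6.4 | Drug discontinuation with reasons, and trial completion, are recorded | Partly: the two are recorded separately, but no conduct rule follows |

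No provision carves reason 2 or reason 4 out of the continuation sentence.

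**Step 2: the samples involved.** Section 5.1 plans four blood samples of 10 mL: 4 × 10 = 40 mL, which matches its stated maximum. One is taken before study drug, leaving 3 × 10 = 30 mL, at 0–24, 48–72 and 96–120 hours after the first dose. Section 4.1 plans sputum before drug and at 72–96 hours, so 2 − 1 = 1 later sample. It plans rectal swabs before drug, at 72–96 and at 144–168 hours, so 3 − 1 = 2 later swabs.

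**Step 3: how the count depends on timing.** Section 8.3 applies only while there is drug left to stop. Dosing every 12 hours for three days (section 1) gives 72 / 12 = 6 doses, at 0, 12, 24, 36, 48 and 60 hours if none is delayed. The samples still scheduled at revocation are:

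| Consent revoked | Blood | Sputum | Rectal |
|---|---|---|---|
| After first dose, before the 0–24 h draw | 3 (30 mL) | 1 | 2 |
| After that draw, before the 48–72 h draw | 2 (20 mL) | 1 | 2 |
| After the 48–72 h draw, before the last dose | 1 (10 mL) | 1 | 2 |

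The first row is the ceiling. Death, comfort care, discharge, or the haemoglobin and transfusion rule in section 5.1 would reduce these counts. If consent is revoked after the last dose, there is no drug to stop and 8.3 does not apply.

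**The case against.** The strongest reply is that 8.3 is about study drug, as its heading says, and that its continuation sentence is the usual protection for intention-to-treat follow-up of patients who stop treatment. On that view section 3.6 governs consent and prevails. Elsewhere the plan ties procedures to consent: section 1 puts the consent process first, and a section 13 footnote requires baseline samples to follow consent. Staff could also omit every later sample without a deviation. As an account of intent this is probably right, and nothing suggests a wish to sample over an objection. It does not cure the wording. Reason 4 is expressly inside the list, the next sentence covers every reason, and nothing says that 3.6 takes precedence.

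Two limits also stand. The explicit right to end participation appears in the EFIC paragraph of 3.6. For other patients, the conflict rests on the ordinary meaning of revoking consent. The consent form is not available for this review, so it cannot be said that it offers no graded withdrawal options; the contradiction between 8.3 and 3.6 exists either way.

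A reader might infer more than the documents support:

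- **Loss of power.** Section 8.3 as written keeps everyone in follow-up, so it loses nobody. A loss could arise only from honouring a withdrawal, and no withdrawal rate is given.
- **Samples or data having to be discarded.** No section says so. That would depend on IRB policy or regulation outside the documents.
- **Families who object only to the drug being recorded as lost for the primary outcome.** No section says so, and drug discontinuation and trial completion are collected as separate items.
- **The first consent conversation always following dosing under EFIC.** Section 3.6 places it after enrolment, and a representative might be reached before the first dose.

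**Conclusion.** The point holds as a contradiction in the text. For reason 4, section 8.3 prescribes follow-up and sampling that section 3.6 allows the representative to end. For reason 2, section 8.3 is inconsistent within itself. This is a stated rule that is wrong as written, not merely a missing detail.

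The size is at most 30 mL of blood in three draws, one sputum sample and two rectal swabs per affected patient. That assumes consent is revoked straight after the first dose, the patient stays in hospital and eligible for sampling, and staff follow 8.3 literally. The number of patients affected cannot be estimated from the documents. The case for changing the text rests on protecting participants and giving sites one rule they can follow, not on any effect on the trial's power.

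**What to change.** Reconcile 8.3 with 3.6, and align 4.1 with both, by separating stopping study drug from withdrawing from the trial. The clinical reasons for stopping drug need not change.

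- Apply the continued follow-up and sampling sentence only to patients who stop drug but remain in the trial. Limiting it to reasons 1 to 3 would not be enough, because reason 2 would still have withdrawn patients sampled.
- Where consent is declined or revoked, or the patient is withdrawn from the trial, stop research sampling. Continue outcome follow-up only as far as the person agrees or the IRB allows.
- Add one case-report field for what was withdrawn: drug only, samples, or all contact. This keeps full follow-up for those who object only to the drug.
- Add withdrawal of consent to the events in 4.1 that end study procedures.

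The cost is a few sentences, one field and a small number of samples forgone.

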3.7. Randomization

A computer-generated allocation sequence will randomize patients in a 1:1 ratio in blocks of six. The clinical trials pharmacist at xxxx will be responsible for randomizing patients independent of study investigators. Based on the randomization, the clinical trials pharmacist will prepare the study drug blinded for delivery to the bedside nurse for administration. At non-xxxx hospitals, the investigators will contact the clinical trials pharmacist at xxxx, or their designee, to tell them of an enrollment. The xxxx clinical trials pharmacist will determine the subject number and complete the randomization.

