9.1. Sample Size

Incidence of EOP without antibiotic prophylaxis is unclear due to low-quality studies, variable definitions for EOP, varying diagnostic criteria, and inconsistent reporting of antibiotic administration. Additionally, studies examine early antibiotics, which may be symptom-driven *or* prophylactic.

In the ANTHARTIC trial, the incidence of EOP at five days was 17% in the prophylaxis group and 31% in controls (absolute difference of 14%).³ When using their definition of EOP, the incidence at seven days was 19% in the prophylaxis group and 34% in controls (absolute difference of 15%).

In the TTM trial, pneumonia occurred in 52% of patients treated at 33°C and 46% in those treated at 36°C.⁶⁵ Pneumonia was not defined as early- or late-onset. In a post-hoc analysis, the incidence of pneumonia in patients admitted to centers administering antibiotic prophylaxis was 41% compared to 54% at centers that did not.⁶⁶ Clustering within centers was possible.

Using data from INTCAR, the incidence of pneumonia, which was not defined as early- or late-onset, was 33% with antibiotic prophylaxis. Accordingly, 60 patients will be randomized to each group (n=120 total). This provides 80% power at a two-tailed 5% level of significance to detect an absolute reduction in the incidence of EOP by 25%, from 55% to 30%.

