9.4. Safety Outcomes

The safety endpoints will be analyzed on an intention-to-treat basis. Safety outcomes will be reported as proportions and study groups compared using the Chi-square test or Fisher exact test, as appropriate.

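### The p<0.05 harm criterion at n=60 has little power for a moderate excess of a single rare event, and the final safety analysis plans no effect estimate or interval

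*Combined protocol and SAP*

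**What the plan says.** Section 8.3 lists the circumstances in which the DSMB may stop the trial. The harm item reads "There is a statistically significant increased risk for serious adverse events". It goes on to include *C. difficile*-associated diarrhoea, gallbladder toxicity and type-one hypersensitivity, and applies "during the interim analysis of the first n=60 patients enrolled. The p-value threshold for harm will be set at 0.05". It does not name a test or its sidedness, and does not say whether event types are pooled or tested one by one. A separate item carries no p-value and no fixed time: "Significant safety concerns emerge and the DSMB and IRB choose to pause or stop the trial".

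For the final analysis, section 9.4 says: "Safety outcomes will be reported as proportions and study groups compared using the Chi-square test or Fisher exact test, as appropriate". It mentions no risk difference, risk ratio or interval. Section 9.2, by contrast, gives early-onset pneumonia (EOP) a risk ratio with a 95% confidence interval.

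The documents give no expected rates for the safety events and no power for the harm criterion.

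**The concern.** For harm, the costly error is to miss a real excess. A p<0.05 criterion on about 30 patients per arm puts nearly all of its error there when events are sparse. Section 9.4 then repeats a significance test without showing how large an excess the data still allow.

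What is at stake is how an unmet criterion is read. Section 2.2 says further study is needed to understand the balance of risk and benefit of prophylaxis, and about 60 more patients are recruited after this look (section 13). If the formal safety results are an unmet criterion at n=60 and p>0.05 at the end, both can be taken as reassurance when they mainly reflect small numbers.

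**Working it through.** **Plan's own figure.** Section 9.1 gives 60 per group: "This provides 80% power at a two-tailed 5% level of significance", for EOP of 55% v 30%. With the pooled-variance formula and mean rate 0.425:

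n = [1.96·√(2·0.425·0.575) + 0.8416·√(0.55·0.45 + 0.30·0.70)]² / 0.25² = (1.370 + 0.569)² / 0.0625 ≈ 60.2, so 61 per arm.

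Power at 60 per arm is 79.9%. The figure reproduces, but it concerns EOP only.

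**Inputs for the harm check.** Allocation is "in a 1:1 ratio in blocks of six" (section 3.7). Sixty patients are 10 blocks, so 30 v 30, assuming one sequence for all sites. The final comparison is 60 v 60 (section 9.1). Event rates are assumptions.

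**Smallest split that meets p<0.05 at 30 v 30, one event type alone.** With all k events on ceftriaxone, the one-sided Fisher p is C(30,k)/C(60,k), and the two-sided p is twice that because the arms are equal.

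- 5 v 0: 142,506 / 5,461,512 = 0.0261, so two-sided p=0.052 (not met).
- 6 v 0: 593,775 / 50,063,860 = 0.0119, so two-sided p=0.024 (met).
- 7 v 1 gives p=0.052 (not met) and 8 v 1 gives p=0.026 (met).

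The count depends on the test, which 8.3 does not name. One-sided Fisher needs 5 v 0 (p=0.026) and uncorrected chi-square 4 v 0 (p=0.038). With 4 to 6 events in all, the expected event count is 2 to 3 per arm, so Fisher is the appropriate choice under 9.4. At 60 v 60, two-sided Fisher again needs 6 v 0 (p=0.027), because 5 v 0 gives p=0.057.

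**Chance of a significant excess on ceftriaxone.** Sum of the product of the two binomial probabilities over all outcomes with more ceftriaxone events and two-sided Fisher p<0.05:

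| Assumed rate, placebo v ceftriaxone | 30 v 30 | 60 v 60 |
|---|---|---|
| 2% v 10% | 4% | 28% |
| 5% v 15% | 9% | 33% |
| 2% v 15% | 18% | 64% |
| 2% v 20% | 41% | 88% |
| 20% v 40% (pooled serious events) | 30% | 60% |

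At 2% v 10% and 30 v 30, one-sided Fisher gives 11% and uncorrected chi-square 22%. The interim look stays weak under any of the three tests. With equal true rates of 2% or 5%, two-sided Fisher fires falsely in at most about 0.1% of trials.

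**What an interval would show.**

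- Zero events in n patients: exact two-sided 95% upper limit = 1 − 0.025^(1/n). This is 11.6% for n=30 and 6.0% for n=60.
- 5/60 v 0/60: difference 8.3%. The Wilson limits are 3.6% to 18.1% for 5/60 and 0 to 6.0% for 0/60. The Newcombe lower limit is 8.33 − √[(8.33 − 3.61)² + 6.02²] = 0.7%. The upper limit is 8.33 + (18.07 − 8.33) = 18.1%. The Fisher p is 0.057.

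In the last case the interval excludes zero although Fisher is not significant, because Fisher is conservative at such counts (uncorrected chi-square gives p=0.022). Under 9.4 a reader would see 8.3% v 0% and a non-significant p-value.

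**The case against.** A reader might infer that serious harm would usually be missed, or that the criterion is a count of six ceftriaxone-specific events against none. The documents support neither.

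- **Scope.** The criterion covers all serious adverse events, with the three named events as examples. The 6 v 0 figure holds for one event type tested alone by two-sided Fisher. If three independent types each ran at 2% v 10% and were pooled, the any-event rates would be 1 − 0.98³ = 5.9% and 1 − 0.90³ = 27.1%. Fisher would then flag the excess 47% of the time at n=60 and 86% at n=120.
- **Large excesses.** The final test detects them often: 88% at 2% v 20%, and 60% at 20% v 40%.
- **Other safeguards.** The DSMB is unblinded (3.10). It receives serious events that meet IRB reporting requirements within five business days, or 48 hours if fatal (8.2). It may act under the safety item without any p-value.
- **Unseen charter.** Section 10.1 places the DSMB charter in a separate document. It may hold further looks or interval displays.
- **Proportions.** Section 9.4 does report proportions by arm, from which a reader could compute an interval.

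All of this stands and limits the point to moderate excesses of a single rare event. It does not supply the missing estimate in 9.4: an interval a reader could work out is not a planned result and does not govern how the safety conclusion is worded. Nor does DSMB discretion stop an unmet criterion being read as reassurance.

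**Conclusion.** The point holds in a limited form. At n=60 the numeric harm criterion has little power for a moderate excess of one rare event: about 4% at 2% v 10% and 9% at 5% v 15% by two-sided Fisher. The final test is significant 28% and 33% of the time in those cases, and 88% at 2% v 20%. The clearer defect is in 9.4, where safety gets proportions and a p-value while the primary outcome gets an effect estimate with an interval.

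The size rests on assumed event rates, a 30 v 30 split at the interim, and Fisher applied to one event type at a time. Pooling or another test raises the power. The conclusion does not extend to harm monitoring as a whole, because DSMB discretion cannot be quantified and the charter was not available.

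**What to change.** In 9.4, report for each safety outcome the risk difference with 95% CI, by a named method (Newcombe or Miettinen-Nurminen), with an exact limit when an arm has zero events. Base any safety statement on the upper limit, not on p>0.05.

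At n=60, show the unblinded DSMB the same counts by arm and intervals. State in 8.3 that not reaching p<0.05 is not evidence of safety.

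No replacement trigger is proposed. A count-based or looser threshold trades misses for false alarms, and the documents give no basis for choosing one.

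The cost is wording in 8.3 and 9.4 and a table in the DSMB report, with no extra patients, data or procedures. The downside is that safety statements will read less favourably: zero events in 60 becomes compatible with a rate of up to 6.0%.
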